Cocaine dependent subjects who respond to advertisements or referrals by phone or in person complete an initial screening process (IRB# HM20000294) asking questions about general inclusion and exclusion criteria at the VCU CARI facility. If subjects appear to meet general inclusion criteria, the research assistant will meet with the potential subject once they have completed the screening protocol in private. At that time, they are asked to participate as volunteer in this study. Subjects who decline to participate will not be coerced in any way. Written informed consent will be obtained from all subjects who agree to research study. Drug dependent subjects who decline to participate or who do not meet inclusion/exclusion criteria will be offered treatment options in the community.

8. * Describe the process for minimizing any potential perception of undue influence to participate when there is a pre-existing relationship between the participant and the researcher (e.g. treatment provider/patient; instructor/student; supervisor/employee, etc.):

The informed consent process involves a detailed verbal description of the study procedures, and how it is used to determine eligibility for participation in the study being conducted at CARI. Staff will emphasize that participation in the study is voluntary. Further, they will be told that they may drop out at any time without penalty or loss of benefits to which they are otherwise entitled. Participants will be informed of procedures for ensuring their confidentiality, including; the use of numbers, codes and/or pseudonyms rather than participants' names;; and the placement of all data in locked files. Participants will be informed that, despite participant confidentiality protections, research staff, under current state law, are required to report certain communicable diseases, and any incidents of sexual or physical abuse of a child or elder. Participants will be given the contact numbers of both the Principal Investigator and IRB Chair to answer questions about the study or one's rights as a human subject. A copy of the signed form is made and given to the client, another copy is held in the Principal Investigator's records, and the original signed consent is kept in a separate, locked file accessible to the Institutional Review Board (IRB) upon request.

9. * How much time will participants be given to make a decision:

The research staff member will meet with the prospective subject in a private room. After receiving a brief overview of the study, the subject will be left alone to review the consent form. After about 5-10 minutes, the research staff member will return and obtain the written consent from individuals who express an interest in participating. Prospective subjects may also take home a copy of the consent form to review before signing it.

10. If applicable, describe the procedures for consenting children upon entering adulthood or participants who are no longer decisionally impaired:

N/A

Consent Groups

1. * Enter a descriptive name for this consent / assent group:

Healthy Control subjects

2. * Select all that apply to this consent / assent group:

Name

Signed Consent by Participant

Signed Parent/Guardian Permission or Legally Authorized Representative Consent

Written/Signed Consent for Genetic Testing

Signed Assent by Child or Decisionally Impaired Adult

Verbal Assent by Child or Decisionally Impaired Adult

Short Form Consent (limited applicability)

None of the Above (select waiver below)

3. * Select all electronic signature platforms that apply to this consent / assent group:

Not using electronic signature platforms

DocuSign Part 11 (FDA regulated studies)

DocuSign (standard platform for non-FDA regulated studies)

REDCap e-Consent

Other electronic signature platform

4. If Other is selected, explain:

5. * Select any waivers that apply to this consent / assent group:

No Waivers Requested

Waiver of All Consent or Some Elements in Consent Form

Waiver of Parental Permission or Legally Authorized Representative Consent

Waiver of All Assent by Child or Decisionally Impaired Adult

Waiver of Signature on Consent/Permission Forms (waiver of documentation of consent)

Exception from Informed Consent (for emergency research only)

6. * Select all study team role(s) that will obtain consent / assent from this group:

Principal Investigator

Co/Sub-Investigator

Medical or Psychological Responsible Investigator

Lead Student/Trainee Investigator (leading their own project)

Research Coordinator

Research Nurse

Consultant

Research Assistant

Pharmacist

Statistician

Regulatory Coordinator

Trainee/Student(working on project)

Other

N/A: Requesting Waiver of Consent

7. * Describe the consent procedures used for this group. Include when, where, and how consent / assent will be obtained both initially and, if applicable, during ongoing participation in the study:

Healthy control subjects who respond to advertisements or referrals by phone or in person complete an initial screening process (IRB# HM20000294) asking questions about general inclusion and exclusion criteria in the CAR1 facility. If subjects appear to meet general inclusion criteria, the research assistant will meet with the potential subject once they have completed the screening protocol in private. At that time, they are asked to participate as volunteer in this study. Subjects who decline to participate will not be coerced in any way. Written informed consent will be obtained from all subjects who agree to research study.

8. * Describe the process for minimizing any potential perception of undue influence to participate when there is a pre-existing relationship between the participant and the researcher (e.g. treatment provider/patient; instructor/student; supervisor/employee, etc.):

The informed consent process involves a detailed verbal description of the study procedures, and how it is used to

determine eligibility for participation in the study being conducted at CARI. Staff will emphasize that participation in the study is voluntary. Further, they will be told that they may drop out at any time without penalty or loss of benefits to which they are otherwise entitled. Participants will be informed of procedures for ensuring their confidentiality, including; the use of numbers, codes and/or pseudonyms rather than participants' names;; and the placement of all data in locked files. Participants will be informed that, despite participant confidentiality protections, research staff, under current state law, are required to report certain communicable diseases, and any incidents of sexual or physical abuse of a child or elder. Participants will be given the contact numbers of both the Principal Investigator and IRB Chair to answer questions about the study or one's rights as a human subject. A copy of the signed form is made and given to the client, another copy is held in the Principal Investigator's records, and the original signed consent is kept in a separate, locked file accessible to the Institutional Review Board (IRB) upon request.

9. * How much time will participants be given to make a decision:

The research staff member will meet with the prospective subject in a private room. After receiving a brief overview of the study, the subject will be left alone to review the consent form. After about 5-10 minutes, the research staff member will return and obtain the written consent from individuals who express an interest in participating. Prospective subjects may also take home a copy of the consent form to review before signing it.

10. If applicable, describe the procedures for consenting children upon entering adulthood or participants who are no longer decisionally impaired:

N/A

Risks, Discomforts, Potential Harms and Monitoring

1. * Describe the risks of each research procedure to participants or others. For each identified risk, provide an assessment of the anticipated seriousness and likelihood of the risk. Some examples of possible risks include but are not limited to:

- Physical risks (e.g. bodily harms or discomforts, side effects, etc.)
- Psychological risks (e.g. emotional, mental, or spiritual harms or discomforts, changes to thoughts, beliefs, or behaviors, etc.)
- Research data risks (e.g. loss of confidentiality and privacy)
- Social or legal risks (e.g. impacts on relationships or reputation, legal or criminal justice actions for self or others, etc.)
- Financial risks (e.g. impacts on income, employability, or insurability, loss of services, etc.)
- Other risks (e.g. unforeseeable risks of experimental procedures, risks related to particular study designs (randomization, washout, placebo, withholding care/services, deception), etc.)

See the help text for additional guidance.

Potential Risks: The primary risks to participation in this study are those related to the single dose of mirtazapine and the risk of MRI and psychological measures. Other risks include psychological (anxiety related to being in the MRI scanner), social risks associated with potential loss of confidentiality, and legal related to potential disclosure of drug related information.

Risks of mirtazapine administration: Mirtazapine is medication approved by the FDA for the treatment of depression. Mirtazapine possible side effects include nausea, dry mouth, constipation, dizziness and feeling drowsy, and worsening of suicidal ideation and elevation of liver enzymes.

Placebo: There are no known serious health risks to treatment with placebo.

Risk of mirtazapine combined with cocaine: Mirtazapine is FDA approved for the treatment of depression and is available for use in patients with depression and cocaine dependence. Previous studies have not reported any serious adverse events of mirtazapine in cocaine dependent subjects (ref). Also, according to clinicaltrials.gov, there are ongoing clinical trials using mirtazapine to treat depression in cocaine dependence.

Potential Risks Not Due To Study Medications

1. Potential risks to participating in this study not involving medication include: unauthorized disclosure of confidential information; discomfort or embarrassment related to urine collection ; possible unwanted encounters with friends or associates.
2. fMRI: Some individuals become anxious due to claustrophobia during MRI scans. This risk will be minimized by having all subjects undergo a "mock" MRI scan using a simulator prior to the actual scan. Subjects with significant claustrophobia during the mock scan will be excluded from the actual MRI study.
3. Individuals who have pacemakers, metal or electromechanical implants or metallic foreign bodies can be injured if they undergo an MRI scan. These individuals will be carefully screened out prior to participation in the MRI experiment by careful history and physical examination, and completion of a standard screening checklist for MRI.
4. Phlebotomy: There is the potential risk of pain and bruising at the site of the blood draw for the HIV test and for the blood chemistries and complete blood count. There is also a slight risk of infection. This risk will be minimized by having blood drawn by a trained phlebotomist.
5. Some subjects who are allergic to tape adhesive may have an allergic reaction to the ECG electrode adhesive. This risk will be minimized by only leaving the electrodes in place for the shortest period necessary to obtain an ECG.

2. * Describe how each of the risks/harms/discomforts identified above will be minimized:

Participants will be evaluated by study physician to screen for physical or psychiatric illnesses or medication interactions that would prevent safe study participation. In order to reduce the potential risk of allergic reaction to the ECG electrode adhesive, electrodes will be left in place for the shortest period necessary to obtain an ECG. Mirtazapine risk of side effects will be minimized by 1) use of a single low dose of mirtazapine 2) screening out any subjects with evidence of suicidal ideation or liver disease. Social and legal risks associated with disclosure of confidential information will be minimized through the use of a 5 digit number to code all information obtained, storage of all information in a locked file cabinet, and obtaining a certificate of confidentiality from NIH to protect against subpoena of research information. All participants will be provided with a 24-hour phone number through which the study physician may be contacted to answer questions or to provide direction in case of emergency.

3. * Describe any potential risks or harms to a community or a specific population based on study findings (e.g. information that could be stigmatizing or derogatory):
N/A

4. Where appropriate, discuss provisions for ensuring necessary medical, professional, or psychological intervention in the event of adverse events to the subjects:

Evaluation of any acute psychiatric consequences from participation in this research will be provided by the study physicians. Treatment for medical and psychiatric consequences of participation in this research is available in the community, and subjects will be referred to appropriate treatment facilities as needed.

5. * Describe criteria for when the investigator would withdraw an individual participant from the study; such as safety or toxicity concerns, emotional distress, inability to comply with the protocol, etc.:

Research participation may be stopped at any time by the study doctor without the subject's consent. The reasons might include:

- the study doctor deems it necessary to protect the subject due to health or safety concerns;
- the subject fails to follow study instructions; or
- administrative reasons require the subject's withdrawal.

6. * Summarize any pre-specified criteria that would trigger the investigator/sponsor/monitoring committee to stop or change the study protocol due to safety concerns:

N/A

Data and Safety Monitoring

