The overall goal of this project is to evaluate the interaction between 5-HT2AR and 5-HT2CR in the functional circuitry underlying impulsivity and cue reactivity associated with cocaine addiction. Specifically, this project will evaluate the role of the 5-HT2CR:5-HT2AR balance in impulsive action and cue reactivity in cocaine-dependent subjects as compared to non-drug using controls. Subjects will be selected based on prescreening for the functionally-relevant 5-HT2CR Cys23Ser SNP. We are currently employing fMRI-based DCM to examine the neurocircuitry of addictions²⁹ given its value in informing the causal influences of one brain region over another underlying behaviors.⁵⁵ In the present project, we will employ DCM to uncover the effective connectivity within nodes of the neurocircuitry involved in impulsivity and cue reactivity

C. Preliminary Progress

1. Impulsivity and cue reactivity are interrelated constructs:

Recent studies support a relationship between behavioral laboratory measures of impulsive action and cue reactivity in both humans²⁷ and animals. We measured impulsivity and cue reactivity in 37 cocaine dependent subjects and 32 non-drug using controls using the Barratt Impulsiveness Scale (BIS), a common clinical instrument for the evaluation of motor impulsivity, a continuous performance test [immediate memory task (IMT)], a behavioral measure of "impulsive action", and the cocaine word Stroop task (cue reactivity). Results revealed that cocaine users had significantly higher impulsivity as measured both by the BIS and IMT, and also had an attentional bias for cocaine-related words on the Stroop task. Within cocaine-dependent subjects, there was a significant correlation between attentional bias and commission errors on the IMT. This correlation between impulsivity and cue reactivity is not simply due to attentional processes as the number of correct detections (a measure of attention) on the IMT does not correlate with attentional bias on the cocaine Stroop. Parallel studies performed in animals demonstrated a positive correlation ($r=0.25$, $p=0.05$) between levels of impulsive action and cue reactivity; this correlation is also unrelated to attentional deficits as % accuracy was identical in high impulsivity (HI) and low impulsivity (LI) rats. These data suggest that impulsivity and cue reactivity are related processes and that there may be an associated underlying neurobiology.

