As the majority of clinical trials run through CAR1 will involve pharmacotherapies and/or behavioral therapies for substance dependence, it is anticipated that study findings (for those trials) will improve our understanding of pharmacotherapeutic mechanisms in substance dependence, and ultimately allow for development of a clinically useful biomarker to aid in the treatment of substance dependence.

5. * Describe any potential for direct benefits to participants in this study:

No direct benefits to subjects are anticipated from taking part in the study.

6. * Describe any potential for direct social impact in this study. For example, any engagement with specific communities to respond to community-identified needs, or ways the study will strengthen the well-being of the specific communities if applicable:

7. Upload a supporting citation list if applicable:

Study Population

1. * Provide the maximum number of individuals that

1. May participate in any study interaction or intervention (Including screening, consenting, and study activities)
AND/OR
2. You obtain any data/specimens about (regardless of identifiability)

at VCU and at other sites under the VCU IRB's oversight. See the help text for additional guidance.
400

2. If this is a multi-Center Project, what is the maximum anticipated number of subjects across all sites?

3. * Provide justification for the sample size by explaining how you arrived at the expected number of participants and why this number is adequate for answering the research questions:

Subjects will consist of 25 male and 25 female subjects with current cocaine dependence and 50 age and gender matched non-drug using control subjects. We expect to recruit and consent approximately 400 subjects to the study. Of these we expect 100 subjects to successfully complete the entire study.

4. * List the study inclusion criteria:

Cocaine Dependent Subjects

To participate in the study, participants must meet the following criteria.

1. Be English-speaking volunteers
2. Be aged between 18 and 60 years
3. Meet DSM-5 criteria for cocaine dependence
4. Have a self-reported history of using cocaine
5. Have hematology and chemistry laboratory tests that are within reference limits (10%) with the following exceptions: hemoglobin and hematocrit within normal limits (for fMRI).
6. Have a baseline EKG that demonstrates clinically normal sinus rhythm, clinically normal conduction, and no clinically significant abnormalities

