- Phone Solicitation scripts (i.e. cold calls or random-digit-dialing)
- Flyers, Mailed Letters or Newspaper/TV/Radio Ads**
- TelegRAM announcements
- Website text**
- Study-specific web sites (provide the design and text)
- Social Media
- EPIC MyChart Patient Portal research study descriptions
- Psychology Research Participant Pool (SONA) study descriptions
- Scripts for announcements made to groups
- Other recruitment material
- No recruitment materials

4. * Describe the study procedures/methods for identifying and recruiting participants. Address the following three aspects of recruitment in your response.

1. Identification of potentially eligible participants or secondary data/specimens of interest.

- What database(s) will be queried to identify secondary data/specimens
- How potential participants' contact information will be obtained

2. Recruitment procedures to invite participation in the study (when applicable):

- How each of the written or verbal recruitment materials and reminders (selected above) will be used
- Who will contact or respond to potential participants
- Locations where recruitment procedures will take place
- The timing and frequency of recruitment attempts

3. Eligibility screening prior to consent and how those activities will be carried out (when applicable)

See the help text for additional guidance.

Potential study participants will be recruited via advertisements and screening procedures described in IRB# HM20000294. At that time, they are asked to participate in the screening evaluation to determine if they are eligible to participate in one of the studies being conducted at CARI. Individuals expressing an interest in participating in the screening evaluation are then consented on the consent form of protocol number HM20000294. Subjects who decline to participate will not be coerced in any way. Written informed consent will be obtained from all subjects. Drug dependent subjects who decline to participate or who do not meet inclusion/exclusion criteria will be referred to treatment options in the community. Once they complete screening evaluation and meet inclusion/exclusion criteria for this study, they will sign an additional study specific consent form to enroll in this study

5. * Does this study have a separate protocol document (i.e. a multisite or sponsor's protocol) that contains a detailed description of the study's methodology?

Yes

No

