6. * Since a separate protocol document is not uploaded, describe the proposed research using language understandable to those IRB committee members whose expertise is not scientific. The description must include:

1. A statement explaining the study design

2. A detailed description of all the procedures that will be followed to carry out the study, preferably in sequential order, and in sufficient detail that the study's methods could be replicated

3. A description of all research measures/tests/interventions that will be used (if applicable)

See the help text for additional guidance

Experimental Design and Methods

Subjects: Subjects will consist of 25 cocaine dependent subjects with the Ser23 HTR2C polymorphism (rs6318 (Cys23Ser / C23S or 68G>C / G68C)) and 25 cocaine dependent subjects with the Cys23 HTR2C polymorphism. In addition 25 non-drug using controls with the Ser23 HTR2C polymorphism and 25 controls with the Cys23 polymorphism will be recruited. Non-drug using controls subjects will have similar age and handedness as the drug dependent subjects. Subjects will be exclusively recruited due to our preliminary data showing group differences on attentional bias based on the HTR2C polymorphism in African American subjects and to reduce heterogeneity. Based on the previously reported prevalence of the Ser23 polymorphism, and our own preliminary data in African American subjects, we expect 13% - 32% of subjects will have at least one Ser23 allele. In order to achieve a balance of subjects with the Ser23 and Cys23 alleles, subjects will be prescreened for the polymorphism according to the schedule below. General inclusion criteria for cocaine dependent subjects includes current cocaine dependence, no current DSM-5 Axis I disorders other than cocaine, marijuana, or nicotine use disorder, or alcohol use disorder (mild to moderate). No past Axis I disorders other than substance abuse/dependence or substance induced mood disorder. No clinically significant non-psychiatric medical disorders. No CNS active prescription medications or other drugs of abuse besides cocaine, marijuana, alcohol, and nicotine.

No metal fragments or implants, and no history of fear of being in closed spaces for MRI scans. Nondrug using controls will have similar inclusion criteria with the addition of any current or past substance abuse or dependence. A detailed list of inclusion and exclusion criteria is provided in the Human Subjects section.

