Subject Recruitment: All subjects will be recruited through the VCU CARI facility.

We anticipate needing to screen approximately 400 subjects over 5 years to obtain the required number of subjects for the study. This will necessitate screening approximately one to two subjects per week. Cocaine-dependent subjects are recruited through advertising in local newspapers and word of mouth. As Richmond has a large cocaine using population, we do not anticipate difficulty recruiting the proposed numbers of subjects.

Overview of Procedures: Subjects will undergo initial screening procedures described in IRB protocol # HM20000294. Eligible subjects will then undergo a baseline mock scan and fMRI scan according to procedures described in Table 1.

Subjects who complete the mock MRI scan without claustrophobia will present at the VCU CARI facility at 7:30 a.m. on the day of the actual fMRI scan and undergo an EKG and urine drug screen. Subjects who have a positive urine drug screen (except cocaine or marijuana) or breath alcohol will be rescheduled.

All subjects must have a negative urine drug screen for all drugs of abuse other than cocaine and marijuana and a negative breath alcohol by Breathalyzer at the time of scanning. Subjects with a positive urine drug screen for cocaine will be evaluated by the study physician for cocaine intoxication. Mirtazapine is FDA approved for the treatment of depression and is available for use in patients with depression and cocaine dependence. Previous studies have not reported any serious adverse events of mirtazapine in cocaine-dependent subjects.⁸⁰ Also, according to clinicaltrials.gov, there are ongoing clinical trials using mirtazapine to treat depression in cocaine dependence. To minimize any risk of the combination of mirtazapine and cocaine, subjects will not be administered mirtazapine who have used cocaine less than 8 hours prior to mirtazapine administration or have any symptoms of cocaine intoxication as determined by a physician. Subjects who smoke cigarettes will be asked to smoke 2 hours before the scan in order to avoid any nicotine withdrawal effects. Subjects who drink caffeinated beverages will be asked to abstain from these beverages prior to the scan. Caffeine and nicotine use will be documented for all subjects.

Subjects who are cleared for drug administration will undergo MRI scans as described below.

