3. * Select all of the methods of blood collection that will be utilized in this study:

- Individual Needle Stick(s)
- Indwelling Catheter Placed Solely for This Study
- Indwelling Catheter Placed for Other Reason(s)
- Blood Collected at the Same Time as Non-Research Blood Collection(s)
- Other

4. * In order to collect urine, will an indwelling catheter be placed solely for the research study:

- Yes
- No

5. * Describe how the sample will be collected and the collection schedule. For each type of sample, include information about

- The procedures that will be followed to collect the sample
- The role(s) of the individuals who will collect the sample
- The volume/size range of the sample
- The timing and frequency of sample collection

A 12-lead electrocardiogram will be used to determine safety during the study. Blood specimens, if not already collected during screening protocol procedure (IRB# HM 20000294, PRE-SCREEN, [name], (PI)), (about 30 cc) will be collected for genetic testing. Blood draws will occur during the screening process (IRB # HM20000294), and will be performed by either the study nurse or one of the study physicians. Drug and alcohol usage will be monitored by obtaining urine and expired air samples

6. * Will genetic testing or analyses be conducted on any of the samples:

- Yes
- No

7. * What are the intended research areas that this DNA will be collected for:

To evaluate the role of molecular interactions between 5-HT2AR and 5-HT2CR in behavioral phenotypes that confer risk for cocaine dependence and relapse. Polymorphisms in the genes encoding the 5-HT2AR and 5-HT2CR receptor subtypes are being evaluated as genetic predictors of treatment for cocaine dependence.

Costs to Participants

1. * Select all categories of costs that participants or their insurance companies will be responsible for:

- Participants will have no costs associated with this study
- Study related procedures that would be done under standard of care
- Study related procedures not associated with standard of care
- Administration of drugs / devices
- Study drugs or devices
- Other

Compensation

1. * Describe any compensation that will be provided including:

1. total monetary amount
2. type (e.g., gift card, cash, check, merchandise, drawing, extra class credit)
3. how it will be disbursed

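### Does the figure of 400 contradict itself across recruitment stages, and is it too small to fill the 50 Ser23 places?

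*Combined protocol and SAP*

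**What the plan says.** The number 400 appears in three places.

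- Study Procedures Q6, Subject Recruitment: "We anticipate needing to screen approximately 400 subjects over 5 years to obtain the required number of subjects for the study", at one to two people per week.
- Study Population Q3: "We expect to recruit and consent approximately 400 subjects to the study", of whom 100 are expected to complete.
- Study Population Q1, a form item answered with 400. It asks for the largest number who "May participate in any study interaction or intervention (Including screening, consenting, and study activities").

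Study Procedures Q4 gives the order of events. General screening takes place, with its own consent, under the separate registry protocol HM20000294. Then, "Once they complete screening evaluation and meet inclusion/exclusion criteria for this study, they will sign an additional study specific consent form". The same answer provides for people who drop out at that point: "Drug dependent subjects who decline to participate or who do not meet inclusion/exclusion criteria will be referred to treatment options in the community".

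On genotype, Study Procedures Q6 (Subjects) asks for 25 Ser23 and 25 Cys23 subjects among the cocaine-dependent and the same among the controls. It says "we expect 13% - 32% of subjects will have at least one Ser23 allele" and that subjects are prescreened to reach this balance. The goal statement in the Background says "Subjects will be selected based on prescreening for the functionally-relevant 5-HT2CR Cys23Ser SNP". Sample Collection Details Q5 allows the genetic blood sample to come from the registry protocol ("Blood draws will occur during the screening process (IRB # HM20000294") or from this study if none was taken earlier. The prescreening schedule and Table 1, to which Q6 refers, are not in the text available for review.

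**The concern.** Two things look wrong.

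The first is the stage. If people are screened, some fail or decline, and only the rest sign the study consent, then the number screened must exceed the number consented. Both are given as about 400, and 400 is also the ceiling for all stages together. Read literally, that leaves almost no room for a screen failure, yet the protocol says what happens to people who fail.

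The second is supply. Ser23 is the scarcer genotype and fills half of the design. If the 400 are counted before genotype is known, the bottom of the carriage range produces barely enough carriers even if none is lost, and the plan gives no eligibility or completion rate for carriers. The cocaine-dependent Ser23 group is the focus of Aims 1 to 3, and the power statement assumes 25 subjects in each group. If that group fell short, the stated power of at least 89% would not apply to the comparison that matters most.

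**Working it through.** **Inputs from the protocol.** 400 people; 5 years; one to two per week; 100 completers; 25 + 25 = 50 Ser23 places; carriage 13% to 32% (midpoint 22.5%). The protocol gives no eligibility or completion rate for carriers, so every such rate below is an assumption.

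**The plan's own pace.** 5 × 52 = 260 weeks, and 400/260 = 1.54 per week, which agrees with one to two. The stated pace covers 260 to 520 people.

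**Can 400 be derived?** No route is given. Dividing places by carriage gives 50/0.13 = 384.6, so 385 people, at the low end and 50/0.32 = 156.25, so 157, at the high end. The first is close to 400 but is not offered as the reason. The figure can be neither reproduced nor called wrong.

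**Break-even.** 50/400 = 12.5%. This applies to carriage multiplied by the share of carriers who qualify and complete, and only if the 400 are unselected on genotype.

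**Expected carriers in 400 unselected people, and the share who must complete to fill 50 places.**

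| Carriage | Expected carriers | Share needed |
|---|---|---|
| 13% | 52 | 50/52 = 96% |
| 22.5% | 90 | 50/90 = 56% |
| 32% | 128 | 50/128 = 39% |

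**Chance of at least 50 carriers, no losses**, from the binomial with n = 400: 64% at 13%, 83% at 14%, 93% at 15%, 98% at 16%, and about 100% at 22.5% and 32%. This allows any split between cocaine-dependent subjects and controls. With an assumed 200/200 split, the chance of at least 25 carriers in both groups is 38% at 13% and above 99.9% at 22.5%.

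**Chance with assumed losses.**

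| Carriage | Assumed completion | Net yield | Chance of 50 |
|---|---|---|---|
| 13% | 90% | 11.7% | 33% |
| 13% | 80% | 10.4% | 10% |
| 22.5% | 70% | 15.75% | 97% |
| 22.5% | 50% | 11.25% | 24% |
| 32% | 50% | 16% | 98% |

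The plan's overall 100/400 = 25% cannot be used as a completion rate for carriers. It may include Cys23 subjects who were set aside only to keep the genotypes balanced.

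**Stages side by side.** If 400 were consents obtained after screening, the stated pace would allow at most 1 − 400/520 = 23% to fail. The text also supports a different count:

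- Initial screening belongs to HM20000294, a separate registry with its own consent (Study Procedures Q4; Data Confidentiality and Storage Q9). People who fail there need not be counted under this study.
- Consent Groups Q7 approaches people who appear to meet general criteria. Genotype is not among the listed inclusion or exclusion criteria, both groups sign a genetic-testing consent, and blood can still be drawn after entry.
- The mock scan takes place in this study and removes people with claustrophobia (Risks Q1).

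On this count about 400 consent to the study, genotyping and the mock scan come next, and 100 complete. The word screen under Subject Recruitment then covers those later steps. The ceiling and the consented number agree without assuming that nobody fails.

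**The case for a change.** The strongest case for a change is that the stage conflict needs no assumption. Subject Recruitment speaks of screening and Study Population Q3 of consenting, with one number for both. Moving registry failures to the other protocol relieves the Q1 ceiling but does not explain why screened and consented are equal. Study Population Q3 also asks expressly how the number was reached, and the answer leaves 300 of the 400 unexplained. Carriage is not yield: the plan itself foresees losses from the mock scan, positive urine screens in controls, pregnancy tests and withdrawal. At 13% carriage, losing more than two of the 52 expected carriers leaves fewer than 50. A stage label and one sentence on the assumed yield would cost almost nothing.

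Much of this stands. The wording is loose, the reading that reconciles it is permitted by the text but not confirmed, the net carrier yield is not stated, and the margin at 13% is thin.

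It does not show that 400 is wrong. The supply argument depends on the 400 being unselected on genotype, which the text does not establish. If genotype is known from the registry before a person is counted, the 13% to 32% applies to the registry and the carrier calculation falls away. The document most likely to settle this, the prescreening schedule, is cited but not in the text, and its absence cannot be held against the plan.

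**Conclusion.** No change is needed. The documents use one approximate recruitment forecast loosely at three stages, and a reader can reconcile them through the separate registry protocol and the genotyping and mock scan that can follow study consent. The carriage range the plan states lies wholly above the 12.5% break-even. With no losses, the chance of finding 50 carriers among 400 unselected people is 93% at 15% carriage and about 100% at the midpoint. A shortfall becomes likely only near 13%, or if carrier completion is low: in expectation, below about 56% at 22.5% carriage or 39% at 32%. Those completion thresholds also assume that the 400 are unselected on genotype.

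Nothing downstream depends on the answer. The target is 25 per group whichever stage the 400 counts, and the power of at least 89% is conditional on those 25, not on how many people are screened to find them. No hypothesis, model or threshold uses the 400. If carriers ran short, it would show during recruitment, and the safety monitoring board is asked to look at recruitment rates. Writing down the stage and an assumed yield would be tidier, but it supplies missing detail and corrects no error.
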